**The effects of the Safe and Sound Protocol on PTSD symptoms and anxiety in trauma survivors:
An observational pilot study**

Updated: March 27, 2025

Background & Rationale

Population-based studies from a range of countries show that a majority of adults will experience a traumatic event at some point in their life (Benjet et al., 2016; Burri & Maercker, 2014) and many of these experiences – such as sexual assault, combat experience, or actual or threatened injury – are known triggers for post-traumatic stress disorder (Kessler et al., 2017). PTSD is defined by a cluster of phenomena that include alterations in brain-body patterns of arousal and reactivity which can manifest in irritability and aggression, hypervigilance, which may be caused or maintained by threat-responsive tuning of the autonomic nervous system (Kolacz, Kovacic, & Porges, 2019). The Safe and Sound Protocol (SSP) is a passive acoustic intervention that is designed as a “neural exercise” to promote efficient regulation of autonomic state. Prior research has shown that the SSP can improve autonomic function, auditory hypersensitivities, and emotion regulation in individuals with Autism Spectrum Disorders (Porges et al., 2013; 2014). Though used by some therapists as part of trauma therapy, there are currently no published studies to document its efficacy for PTSD symptoms or comorbidities. This current observational pilot study is being conducted to establish methods for an upcoming randomized controlled trial to test the utility of the SSP for trauma treatment.

Study Procedures

All participants, regardless of study arm, will be recruited from the pool of Spencer Psychology clients who are actively receiving psychotherapy. Participants will continue to receive weekly or bi-weekly psychotherapy during the course of the study. In both arms, participants complete surveys that assess PTSD symptoms (PCL-5), anxiety symptoms (GAD-7), and, autonomic symptoms (BPQ) over the course of 4 timepoints.

Psychotherapy + SSP Arm

After having received an email from the potential subject indicating interest in participation, subjects will be screened online via email to ensure they meet eligibility criteria for the study. If client meets eligibility criteria for study, they will be contacted by a research assistant to schedule their first visit prior to beginning the SSP. Participants will be given an option of either scheduling a session at an Indiana University laboratory building or at Spencer Psychology, where they receive therapy.

When the participant arrives, they will complete a standard COVID-19 screener inside the entrance hallway. Masks will be worn by researcher and participant during the protocol as long as these are part of official state and university guidelines. Masks may be removed if research assistants and participant have proof of complete vaccination. If participant has symptoms or has been in contact with someone likely to have COVID-19, the visit will be rescheduled. If participant passes the screening, they will be led to the laboratory.

Visit 1. The researcher will describe the study, offer to read through the consent form with the participant or have the participant read the consent on their own, and answer any questions. If client consents, data collection will begin.

The participant will complete a set of surveys self-reporting demographics, comorbidities, and psychological well being via Qualtrics on a laptop provided by the researcher (~15 minutes). The RA will then guide the participant through physiological data collection using the iom2 ear clip. Participants will be given instructions on how to put on the earlobe sensor, which attaches via an

ear clip. To stabilize the iom2 cable, an additional clip may be used to attach the iom2 to clothing, waist, or it would be secured on a lab-provided shoulder holster. Once sensor is in place, a researcher will connect the iom2 device to a laptop and begin recording.

The participant will then be cued by a video to move into 3 postures for 3 minutes each: lying down on a cot, sitting up, and standing. After the final posture, the participant will be instructed to remove the measurement device. The device, the cot, and the chair will be sterilized after use with soap and water or other cleaner.

At completion of the first visit, participants will be provided the first \$25 Amazon gift card and reminded of the incentive schedule. If the participant knows when their SSP administration will begin, they will be scheduled for their next visit which will take place 1 week after their final listening session. If start date is unknown, the participant will be contacted in 3 weeks about scheduling visit 2.

SSP Sessions and Data Collection

The Safe and Sound Protocol (SSP) will be delivered with 5 hours of increasing frequency modulation over time, as used in prior studies (Porges et al., 2013; 2014), using a phone-based app. Participants will have a choice of 2 music playlists, one that featured popular adult contemporary music and one that primarily featured music from children's movies. Frequency filtering will be applied to playlists using the Safe and Sound Protocol (SSP) using an algorithm to alternate narrowing and expanding the range of acoustic frequencies over time, with the alternations intensifying in frequency range over the course of the music tracks. The filtering is optimized for the frequency response of adult human hearing and intended to mimic the expression of the human voice around a central set of frequencies of 800-1200 Hz. The results of the filtering method are similar to adjusting the treble and bass settings on a stereo system while music is playing; the melody and instruments can still be heard, but the highest and lowest pitches are modulated over time. Music listening will be conducted with high-fidelity, closed-back, over-the-ear headphones while seated. The headphones had a flat frequency response to accurately reproduce music frequencies. The sessions will aim for 30 minutes of listening in each 1-hour session to permit opportunity to discuss client response, and support shifts that happen during listening. The 30 minutes of listening may be discontinuous, with client and therapist each having the possibility to stop the music at any point to discuss and may resume when client is ready. If agreed on by the participant and therapist, some listening time will be completed either at home or in a listening room provided by Spencer Psychology. The room is for those who do not have a distraction-free space and/or over-the-ear headphones at home

Therapists will report on total listening minutes during the session and notes on client response into their standard session reporting form. Spencer Psychology will provide these portions of the session notes to the research team. Researchers will not have access to any additional therapist notes on the client.

Visit 2. The week after the client completes their 5th hour of SSP, a second assessment will be scheduled. As part of this assessment, the client will complete the survey post assessment on the laptop (~10 minutes) and pulse data collection using the iom2 during supine, sitting, and standing postures. Upon completion, the participant will schedule their 4-week post appointment. They will then receive their second \$25 Amazon gift card and be reminded of the incentive schedule.

Visit 3. Five weeks after their final SSP session, participants will return for their last assessment. They will then complete the survey post assessment on the laptop (~10 minutes) and pulse data

collection using the iom2 during a supine-sit-stand challenge using the same procedures as previous visits. They will then receive their third \$25 Amazon gift card, and another \$25 Amazon gift card if they've completed all three assessments.

Data collection from Spencer Psychology medical records.

The study team will receive medical records from Spencer Psychology. Spencer Psychology has a secure, internal database that Spencer Psychology staff will program to output required information. Unique study IDs will be assigned to participants and medical records will be exported and stored with these IDs, not with the names of the participants. We will collect the following information from medical records: Gender, Birth date, Intake and treatment information (date, diagnosis, therapy goals, medication use), session information during SSP administration information (length of use during session), mood and cognitive features during the visit, Changes in treatment objectives, goals, and diagnosis, Clinician comments on visit.

Treatment as Usual (Psychotherapy Only)

If they are interested in participation, they will contact the study team by email provided in the recruitment materials. The study team will send out a link to a screener survey that contains the PCL-5 post-traumatic stress questionnaire. The screener will be used to match this sample to the distribution of the PTSD symptom severity in the SSP study. If eligible for the study based on the screener, the participant will receive an email invitation to participate in the full study, including a link to the survey which contains the Informed Consent Statement and the first full survey.

Subjects will then complete the first survey, which will ask about demographic information; email address for follow up surveys; caffeine, alcohol, nicotine use; medication use; therapy history; PTSD, anxiety, and autonomic symptoms. The survey will close with a statement describing the timing of their next assessments when they will receive the email invitation to complete their next survey, who to contact if they do not receive that email, and that they will receive their digital gift card code via the email address they provided in the survey.

After subjects have consented and completed the first survey, the study team will receive the following information from Spencer Psychology: gender, intake date, diagnosis, client therapy goals. The study team will also receive the following information from session notes for the duration of the study: mood and cognitive features during visits, changes in treatment objectives, goals, and diagnosis, clinician comments on visits.

Questionnaires that assess PTSD symptoms, anxiety symptoms, and, autonomic symptoms will be used for measuring main outcomes. The timeline of surveys was based on average length of SSP listening completion from the SSP+Psychotherapy arm:

1. Survey 1 (10-15 minutes)
2. Survey 2 (5-10 minutes, 45 days after survey 1)
3. Survey 3 (5-10 minutes, 45 days after survey 2)
4. Survey 4 (5-10 minutes, 30 days after survey 3)

Incentives

Participants in the music listening group were compensated up to a total of \$125: a \$25 gift card for each lab visit and corresponding survey, and an additional \$25 gift card for completing all the assessments. Participants in the treatment as usual group were compensated up to \$50: a \$10 gift card for each of the 4 surveys they completed, with an additional \$10 for completing all of the surveys.

Statistical Plan

The goal of the study is to collect exploratory pilot data to inform a large randomized study in the future. Due to the novel nature of the research question there is no prior data to inform power analysis. Results from this small study will be used for power estimates for the upcoming planned randomized study. All efforts will be made to avoid missing data. Research assistants will track potential reasons for missing data in order to strengthen procedures in the follow up study and reduce missing values. Quality assurance steps for data collection will include: Monthly meetings with RAs to visualize and review incoming data, automated range checks, and comparing redundant items that are included in both medical records and self-reports for convergence (e.g., age). Change over time will be modeled using mixed effects modeling with maximum likelihood, which uses all available data on predictors even when some values are missing. Support for non-zero parameters will be indicated by 95% confidence intervals excluding zero. In the SSP+psychotherapy group, earlobe pulse data will be used to quantify inter-beat intervals using automated peak detection with manual checks for accuracy. These will be analyzed for mean heart period and respiratory sinus arrhythmia using previously published methods (Porges, 1985; 1986; Lewis et al., 2012).

References

Brady, K. T., Killeen, T. K., Brewerton, T., & Lucerini, S. (2000). Comorbidity of psychiatric disorders and posttraumatic stress disorder. *Journal of clinical psychiatry*, 61, 22-32.

Burri, A., & Maercker, A. (2014). Differences in prevalence rates of PTSD in various European countries explained by war exposure, other trauma and cultural value orientation. *BMC Research Notes*, 7(1), 407. doi:10.1186/1756-0500-7-407

Kessler, R. C., Aguilar-Gaxiola, S., Alonso, J., Benjet, C., Bromet, E. J., Cardoso, G., . . . Survey, W. W. M. H. (2017). Trauma and PTSD in the WHO world mental health surveys. *European Journal of Psychotraumatology*, 8(1), 1353383. doi:10.1080/20008198.2017.1353383.

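### The triggers for the SSP post assessments differ for participants who stop listening early, while treatment as usual is surveyed on fixed days, so SSP follow-up could over-represent completers

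*Combined protocol and SAP*

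**What the plan says.** SSP participants enrol and give baseline data before listening starts. Under Psychotherapy + SSP Arm, "they will be contacted by a research assistant to schedule their first visit prior to beginning the SSP".

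Visit 2 is then described in two places:

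- Under Visit 2: "The week after the client completes their 5th hour of SSP, a second assessment will be scheduled".
- In the text closing Visit 1, for a participant whose start date is known: "they will be scheduled for their next visit which will take place 1 week after their final listening session". For the rest: "If start date is unknown, the participant will be contacted in 3 weeks about scheduling visit 2".

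The Visit 3 paragraph reads: "Five weeks after their final SSP session, participants will return for their last assessment". The only step described for booking it is in the Visit 2 paragraph: "Upon completion, the participant will schedule their 4-week post appointment".

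Under Treatment as Usual (Psychotherapy Only), surveys are spaced at fixed intervals of 45, 45 and 30 days. The reason given is: "The timeline of surveys was based on average length of SSP listening completion from the SSP+Psychotherapy arm". That arm is also selected on baseline severity: "The screener will be used to match this sample to the distribution of the PTSD symptom severity in the SSP study".

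The Statistical Plan models change with a maximum-likelihood mixed model on all available data, promises every effort to avoid missing values, and has reasons for missing data tracked. The results are to supply power estimates for a planned randomised trial. The plan names no time variable, gives no rule for following SSP participants who do not finish, and describes no sensitivity analysis for them.

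**The concern.** In one arm, whether a participant is assessed after baseline may depend on finishing the intervention. In the other arm it depends only on the calendar. If the 5th-hour wording is followed literally, SSP participants who stop early may contribute a baseline and nothing else, while TAU clients are invited to every survey however their therapy goes. Matching the arms on baseline PCL-5 severity does not cure this, because the match concerns who enrols, not who is later measured.

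Maximum likelihood removes the resulting bias if stopping depends only on data in the model. For a stopper without Visit 2, that may mean Visit 1 scores alone. If stoppers do worse than completers with the same baseline, the SSP benefit is overstated. If they stop because they feel better, it is understated. Tracking reasons for missingness helps interpretation but supplies no outcome. The pilot exists to inform the size of the next trial, so an error in either direction could carry over into it.

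**Working it through.** **1. The triggers side by side.**

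| Participant | Visit 2, 5th-hour wording | Visit 2, text closing Visit 1 | Visit 3 |
|---|---|---|---|
| Finishes 5 hours | 1 week after | 1 week after (same) | 5 weeks after; agrees with 1 week + 4-week appointment |
| Stops early | Not triggered | 1 week after last session | Due 5 weeks after last session; only booking step described follows Visit 2 |
| Never starts, start date known at Visit 1 | Not triggered | May hold an advance booking | No final session to count from |
| Never starts, start date unknown | Not triggered | Contact at 3 weeks, no assessment date | No final session to count from |

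TAU: day 45; 45 + 45 = day 90; 90 + 30 = day 120.

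**2. How many SSP assessments there are.** Visits 1 to 3 make three, but Study Procedures gives four timepoints for both arms. Three visits would pay 3 x $25 + $25 = $100, and four would pay 4 x $25 + $25 = $125, which is the maximum stated under Incentives. The gap from Visit 2 to Visit 3 is 35 - 7 = 28 days, close to the 30 days between TAU Surveys 3 and 4. An undescribed mid-course SSP assessment is therefore plausible but not shown.

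**3. Spread of SSP timing.** Five hours at the intended 30 minutes per session is 300 / 30 = 10 sessions. Assume all listening is in session, and read bi-weekly as every two weeks. Counting from the first listening session:

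- Weekly: last session at 9 x 7 = day 63, Visit 2 at day 70, Visit 3 at day 98.
- Two-weekly: last session at 9 x 14 = day 126, Visit 2 at day 133, Visit 3 at day 161.

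Home listening shortens these times. A wait between Visit 1 and the first session lengthens the time from baseline.

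**4. Bias if only completers have post data (illustration; all inputs assumed).** Bias = share stopping x baseline-adjusted gap in mean change. For a gap of 10 PCL-5 points: 0.1 x 10 = 1, 0.2 x 10 = 2, 0.3 x 10 = 3 points, of either sign.

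**5. What maximum likelihood does.** A simulation used one baseline and one post score, unit SD, correlation 0.6 and no true change, with the post score missing for every non-completer. When completion depended only on baseline, the estimate was within 0.002 SD of the truth. When worse unobserved post scores made completion less likely, it was too favourable by 0.07, 0.13, 0.19 and 0.25 SD at 10, 20, 30 and 40% non-completion. Reversing that dependence would reverse the sign.

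**6. Consequence for the next trial (illustration; all inputs assumed).** Suppose that trial counts everyone randomised, is sized at 80% power on the completer effect and makes no allowance for non-completion. Let p be the share stopping, f the stoppers' benefit divided by the completers' benefit, and k = 1 - p(1 - f). Then power = Phi(2.80k - 1.96), and the N needed is 1/k² times the planned N.

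| p | f = 0.5: k, power, N factor | f = 1.5: k, power, N factor |
|---|---|---|
| 0.1 | 0.95, 76%, 1.11 | 1.05, 84%, 0.91 |
| 0.2 | 0.90, 71%, 1.23 | 1.10, 87%, 0.83 |
| 0.3 | 0.85, 66%, 1.38 | 1.15, 90%, 0.76 |

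At f = 1, k = 1 and power stays at 80% for any p.

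**The case against.** The best defence is that the plan already reaches stoppers. Two of the three wordings count from the final session, and the 5th-hour sentence may simply describe the usual case. Much of this stands, and it rules out several stronger readings that a reader might infer.

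- **That early stoppers are excluded.** This follows only if the 5th-hour wording governs, and nothing says that it does. Nothing says that it does not, so staff would have to choose.
- **That missing Visit 2 removes Visit 3.** Visit 3 is worded without condition. Its bonus for completing all three assessments makes sense only if someone can attend after missing one. What remains is that no other booking route is described.
- **That no never-starter has a date.** Where the start date is known, Visit 2 is booked at the end of Visit 1, so some may hold one.
- **That stoppers have only baseline outcomes.** A fourth, mid-course assessment would give some of them post-baseline data.
- **That the arms are assessed at different average times.** TAU dates were set from average SSP completion time, so the documents do not support a timing bias in the arm means. Individual SSP timing still varies.

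The plan also has monthly data review, and session notes give some information on stoppers. These are not PCL-5, GAD-7 or BPQ scores, and no analysis use is stated for the notes. Finally, this is an exploratory, non-randomised pilot. That limits the weight of the point but does not remove it, because the estimates are to be reused for power.

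**Conclusion.** The concern holds as a gap in the follow-up rules. The wordings agree for completers and diverge for early stoppers. Never-starters whose start date was unknown at Visit 1 have no assessment date. TAU follow-up does not depend on the course of therapy. SSP post-baseline data could therefore over-represent completers, and maximum likelihood protects only if stopping depends on observed data.

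It would go too far to conclude that the SSP effect is overstated, or that the estimate is a completer estimate. The documents give no stopping rate and no outcomes for stoppers, so size and direction are both unknown. The bias and power figures rest wholly on assumed inputs, and the power figures further suppose that the next trial makes no allowance for non-completion. Confidence is medium. The change is worth making because it is cheap and the results feed the sizing of the randomised trial.

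**What to change.** 1. Reconcile the wordings so that post assessments are due after the last listening session, whether or not 5 hours were reached, and book Visit 3 independently of Visit 2. Send the existing online survey on a fixed backstop date (for example day 120 from Visit 1, the last TAU date) to any enrolled SSP participant without Visit 2. This will also reach slow listeners, so record listening status: never started, stopped, continuing or complete. Analyse everyone enrolled.
2. Name actual days since baseline as the time variable in both arms.
3. If SSP collection is over, as the past tense under Incentives suggests, report how many SSP participants lack post-baseline data, with their listening status and recorded minutes. Only in-session minutes are described, although listening elsewhere is allowed. If the number is not negligible, describe the estimate as mainly from completers and show its sensitivity to shifts in both directions for non-completers before using it to power the randomised trial.
4. Reconcile the four timepoints and the $125 maximum with the three SSP visits described, and give the timing of any further assessment.

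Cost: one status field, one short sensitivity table and, if collection is open, one short survey for some participants at $10 (TAU survey rate) to $25 (SSP visit rate) each. Downsides are some added burden, some outcomes collected online rather than in the lab, and a possibly less favourable SSP estimate.

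### Does leaving open which pilot results will feed the RCT power estimates call for a change to this plan?

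*Combined protocol and SAP*

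**What the plan says.** The Statistical Plan describes an exploratory pilot: "The goal of the study is to collect exploratory pilot data to inform a large randomized study in the future". It explains why it gives no sample-size calculation of its own, "Due to the novel nature of the research question there is no prior data to inform power analysis", and then states the onward use: "Results from this small study will be used for power estimates for the upcoming planned randomized study". Change over time is to be estimated by mixed models fitted by maximum likelihood. The rule for interpretation is "Support for non-zero parameters will be indicated by 95% confidence intervals excluding zero".

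Three other places bear on the point. Under Study Procedures, for both arms: "Participants will continue to receive weekly or bi-weekly psychotherapy during the course of the study". Under Treatment as Usual (Psychotherapy Only), the comparison arm has a PCL-5 screener: "The screener will be used to match this sample to the distribution of the PTSD symptom severity in the SSP study". The same section names the outcome families without ranking them: "Questionnaires that assess PTSD symptoms, anxiety symptoms, and, autonomic symptoms will be used for measuring main outcomes".

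The document does not say which outcome, timepoint, contrast or variance component will go into the later power calculation. It gives no pilot sample size, and no target difference or power for the randomized trial.

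**The concern.** Informing a randomized trial is a stated purpose of this study, and the plan says that no earlier data exist. A reader may therefore suppose that the effect seen here will become the target difference. There are two candidates, and both are weak.

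- **Difference between arms.** It comes from a small study, so it is imprecise. The arms are not randomized, so it can be confounded in a direction that nobody can state. Assessment times differ too: SSP visits fall one and five weeks after listening ends, while the comparison arm is surveyed at fixed intervals of 45, 45 and 30 days.
- **Pre-post change in the SSP arm.** Psychotherapy continues throughout, so this change includes whatever clients gain from psychotherapy alone. If they do gain, it overstates what SSP adds.

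A trial sized on either could be far too small to detect the true effect or, if the estimate fell low, several times larger than needed.

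**Working it through.** The plan has no power figure to reproduce, so the check asks two things: how large the harm would be if the observed effect were used, and whether the plan's wording leads there.

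**Inputs.** All are assumptions, because the documents give none: true standardized difference d from 0.3 to 0.8; 15, 20 or 30 per pilot arm; randomized trial at two-sided 5% and 80% power, 1:1, no dropout.

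**Precision of the pilot effect.** The 95% half-width is 1.96 × √(2/n), which is 0.72, 0.62 and 0.51 SD for n = 15, 20 and 30. This is an unadjusted comparison. If the SD is cross-sectional and the model adjusts for a baseline correlated 0.7 with the outcome (assumed), multiply by √(1 − 0.49) = 0.714, giving 0.51 down to 0.36.

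**Sizing on the observed effect.** Size per arm is m = ceil[2 × (2.8016/d̂)²] + 1. True power is Φ(d√(m/2) − 1.96).

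One case: d = 0.5 and 20 per arm. The size needed is ceil(62.8) + 1 = 64. The standard error of d̂ is √(2/20) = 0.316, so its quartiles are 0.5 ± 0.6745 × 0.316 = 0.287 and 0.713.
- Upper quartile: m = 32, and power is Φ(0.5 × 4 − 1.96) = 52%.
- Lower quartile: m = 192, three times the need.

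Simulation of 400,000 pilots per setting, restricted to those with a positive effect:

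| True d | n per arm | Power < 80% | Power < 50% | Power > 95% |
|---|---|---|---|---|
| 0.3 | 15 | 63% | 45% | 28% |
| 0.3 | 30 | 57% | 35% | 32% |
| 0.5 | 15 | 54% | 28% | 33% |
| 0.5 | 30 | 50% | 19% | 32% |
| 0.8 | 15 | 48% | 14% | 32% |
| 0.8 | 30 | 46% | 6% | 26% |

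Over all pilots, 46% to 50% lead to a trial below 80% power. That figure is nearly automatic: sizing on any median-unbiased estimate falls short about half the time, whatever the pilot's size. The two tails are the informative part.

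**Sizing on the pre-post change.** Suppose SSP adds 0.4 SD and psychotherapy alone gives 0.1, 0.2 or 0.3 SD (assumed). Sizing on the sum gives m = 64, 45 or 34, and power at 0.4 is 62%, 48% or 38%.

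**Sizing on a fixed target.** Take only the SD from the pilot, at its upper one-sided 80% limit (multiplier 1.14, 1.12 or 1.09 for 15, 20 or 30 per arm, pooled over arms). The result depends on how close the target lies to the truth:

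| Target | True d | Result over 15 to 30 per arm |
|---|---|---|
| Equal to true d | 0.3 to 0.8 | 12% to 19% below 80% power |
| 0.5 | 0.4 | 78% to 94% below 80% power |
| 0.5 | 0.3 | all below 80%; 58% to 76% below 50% |
| 0.4 | 0.5 | 74% to 76% above 95% power |

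The first row is a best case. A smallest worthwhile difference is a sound target because missing a smaller effect is acceptable. It does not secure power at an unknown true effect.

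**Does the wording lead to the harm?** The plan promises that results will inform power estimates. An SD, a within-person correlation and an attrition rate are all results, and a power calculation needs them. No sentence says that an observed difference will be the target. The harm therefore needs a step that the document does not take, in a trial that this document does not govern.

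**The case for a change.** The strongest case for a change is that the omission is real, bears on a main purpose of the study, and could be closed in a few sentences without touching conduct. With no prior data, the observed effect is the obvious default, and nothing rules it out. The calculations above show that this default would be poor in both directions, across every pilot size and effect considered.

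Much of that stands: the gap exists, and the observed effect would be a bad target. Three things weaken the case for amending this plan.

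- The choice of target belongs to the randomized trial's protocol, where it must be justified in any case.
- A rule written here would have to pick an outcome and a timepoint that the plan leaves unranked, and to pool the SD of change over arms assessed on different schedules. A requirement to fix the target before the pilot outcomes are examined may no longer be achievable. The severity matching implies that SSP-arm PCL-5 data were already in use, and of the survey schedule the plan says "The timeline of surveys was based on average length of SSP listening completion from the SSP+Psychotherapy arm".
- The screener is weak evidence of confounding. A PCL-5 matching screener is described only for the comparison arm, but SSP candidates are also screened, by email, against criteria that the document does not list. Matching on severity tends to reduce imbalance.

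**Conclusion.** No change to the plan follows. It omits a detail about a later trial's sample size and states no rule that gives a wrong answer. The same participants, data, models and intervals result whether or not the detail is added, and the intervals already planned will show how imprecise the effects are.

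The possible harm is large only on a condition the documents never state, that the observed effect becomes the target. Even then, the size of 6% to 45% below half power rests on an assumed pilot size, true effect and trial power, and it shrinks as the pilot or the effect grows.

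Anyone designing the randomized trial would be expected to take the SD, within-person correlation, attrition and listening completion from this pilot with their uncertainty, and to justify the target difference separately. The present wording allows exactly that. The point is minor and belongs in the review of the randomized trial's protocol.

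### Does crediting maximum likelihood with handling missing predictors, rather than missing outcomes, leave a gap in the analysis?

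*Combined protocol and SAP*

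**What the plan says.** The Statistical Plan in the combined protocol and SAP has one statement on how the analysis copes with incomplete data. It specifies "mixed effects modeling with maximum likelihood, which uses all available data on predictors even when some values are missing". Its other text on the subject concerns preventing gaps, logging the reasons for them, and quality checks, one of which is "comparing redundant items that are included in both medical records and self-reports for convergence (e.g., age"). It lists no covariates, names no missingness mechanism, and describes neither imputation nor a joint model for predictors. It gives no sample size and presents the study as exploratory.

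The outcomes are questionnaire scores. Under Treatment as Usual: "Questionnaires that assess PTSD symptoms, anxiety symptoms, and, autonomic symptoms will be used for measuring main outcomes".

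Background variables come from different sources in the two arms. In the SSP arm, the medical-records subsection lists "Gender, Birth date, Intake and treatment information (date, diagnosis, therapy goals, medication use", among other items. In the comparison arm, the records supply "gender, intake date, diagnosis, client therapy goals" and some session-note items, while the first survey asks about "caffeine, alcohol, nicotine use; medication use; therapy history". No section says that any of these enters a model.

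Background & Rationale says that the pilot "is being conducted to establish methods for an upcoming randomized controlled trial".

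**The concern.** The usual merit of likelihood-based mixed models is that people with some missing outcome waves stay in the analysis, with valid inference if those outcomes are missing at random. That merit does not extend to missing predictors. A reader who took the sentence at face value could add medication use or therapy history to the model and assume that gaps in it needed no attention. Standard software would instead drop every row of each affected person, including outcomes that had been observed.

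Two features make this look more serious. The sentence is the plan's only analytic statement on missing data, and the pilot is meant to set methods for a later randomized trial, so an inaccurate description could be carried forward. At stake would be precision, and possibly an unequal loss between arms if gaps in one arm could be filled from records and gaps in the other could not.

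**Working it through.** The plan states no figure that could be reproduced here, so the check is of the method, followed by what the method implies for the plan as written.

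**1. What the likelihood does.** For participant *i*, a standard mixed model contributes f(y_i,obs | X_i, θ), which is the integral of f(y_i,obs, y_i,mis | X_i, θ) over the missing outcomes. Missing outcomes integrate out and the observed ones remain. X_i is conditioned on, so a row with an unknown element of X has no defined contribution unless X is given its own model or is imputed.

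**2. Illustration (assumed: 60 people, 4 waves, one baseline covariate).** Total rows are 60 × 4 = 240.
- Outcome missing at the last two waves in 12 people: 240 − 12 × 2 = 216 rows, and all 60 people are kept.
- Covariate missing in the same 12 people: 240 − 12 × 4 = 192 rows and 48 people, with 48 observed outcomes discarded.

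The technical point is therefore right.

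**3. Use of data versus validity.** In 300 simulated sets of 200 people with a true slope of −2.00, the mean maximum likelihood slope was −2.01 with full data, −2.02 with outcomes missing at random, and −2.63 with outcomes missing not at random. The fit uses every observed outcome in all three settings. Missing at random is the condition for valid inference, not for using the data. Rewording the clause alters neither behaviour.

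**4. Predictors in the plan as written.** The only predictor in the text is time, through the reference to change over time; arm is implied by the two-group design. Arm is fixed at recruitment and time is known for each completed assessment. Rows lost to missing predictors: 0.

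**5. If an incomplete covariate were added.** Suppose a fraction q of people in each arm lacks it, unrelated to anything else, and nothing is done. The variance of the arm-by-time term scales with 1/(1 − q), so its standard error is multiplied by √(1/(1 − q)):
- q = 5%: √(1/0.95) = 1.026
- q = 10%: √(1/0.90) = 1.054
- q = 20%: √(1/0.80) = 1.118

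The rates, and the presence of such a covariate, are assumptions.

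**6. Could the loss differ by arm?** Take medication use. In the SSP arm it appears in the records list, while the Visit 1 description of the self-report surveys does not mention it. In the comparison arm it appears in the first survey and not in the records list. The document therefore shows no overlap of survey and records for medication in either arm, so the convergence check on redundant items does not bear on it. A contrast between filled gaps in one arm and unfilled gaps in the other would need an SSP-arm medication question that the document does not show. What it shows is a different source in each arm, which is a separate matter from missing predictors.

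**7. Row counts for this study.** These cannot be fixed. Study Procedures gives four timepoints for both arms, while the SSP arm describes three visits. The Incentives maximum of $125 fits four visits (4 × $25 + $25), whereas three would give 3 × $25 + $25 = $100. Nothing in steps 1 to 6 depends on which is right.

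**The case for a change.** The best case for editing the sentence is that it is inaccurate on its literal reading, costs a sentence or two to correct, and sits in a study meant to set methods for a later trial. If missing outcomes were meant, the word is wrong; if a likelihood that also models covariates was meant, the plan does not describe one.

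The accuracy point stands for the literal reading. The remainder is weaker. The clause does not say which values are missing, and it can fairly be taken to mean that a person's predictor data still contribute when an outcome wave is absent, which is what these models do. It does not say that incomplete predictors need no handling. The later trial will need its own analysis plan with its own covariates, and the pilot's rationale clause does not bind it. An analyst who added an incomplete covariate would see the reduced number of observations in the output and would have several acceptable options: report the loss by arm, fill from records, impute, or model jointly. A list of predictors is a request for more model detail, and in an exploratory pilot its absence is a gap that analysts fill sensibly.

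**Conclusion.** No change to the plan is needed. The clause is loosely worded, most likely a clerical slip for outcomes, and it explains the choice of model without specifying any step of the analysis. Correcting it would change no fitted model, estimate or confidence interval. With time and arm as the only predictors, the effect is nil.

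This conclusion assumes that no incompletely observed covariate enters the main models, or that its gaps are handled and reported if one does. If that assumption failed in both arms, the cost would be mainly precision: about 2.6% to 11.8% on the standard error for assumed losses of 5% to 20%. The document does not support a claim that the loss would fall unequally on the arms.
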